# 6.1.1 Safety Review Committee/Data Monitoring Committee

All aspects of the study will be carefully monitored with respect to GCP and SOPs for compliance with applicable government regulations. The Study Monitor will be an authorized individual designated by the Sponsor. The Study Monitor will have access to all records necessary to ensure integrity of the data and will periodically review the progress of the study with the Principal Investigator.

12

Weeks

#### 6.1.2 Justification of Sample Size

Placebo arm

Interim analysis of ERP-P300 latency when 30 subjects complete Week 2

A total sample size of 75 evaluable subjects (25 per treatment arm) was chosen empirically for this proof-of-concept study based on ERP P300 latency results obtained in the Phase 1a/b study, NDX-1017-0101; no formal sample size calculation was applied.

#### 6.2 **Efficacy Measures**

A qualified, trained, and certified rater will administer questionnaires to the study subject and/or dedicated support person/caregiver.

Confidential Page 15 of 57

#### 6.2.1 Cognitive Variables & Pharmacodynamic Variable

## 6.2.1.1 Global Statistical Test (GST) score

A composite approach will be used to facilitate the assessment of an overall change in disease status/trajectory in the trial. The GST score will be defined as a single outcome variable based on standardizing and then combining individual patient-level change from baseline cognition (ADAS-Cog13) and change from baseline in ERP P300 latency. The GST score will be determined for each patient at each time point and the resulting scores will define the efficacy outcome variable to be used in the primary efficacy analysis. A formal definition of the GST score is given in Appendix 1. The assessment will be performed as per Appendix 2 Schedule of Assessment.

#### 6.2.1.2 Alzheimer's Disease Assessment Scale – Cognitive Subscale (ADAS-Cog13)

The ADAS-Cog13 is designed to measure cognitive symptom change in subjects with MCI as well as AD (Mohs et al, 1997). In addition to the standard 11 items present in the ADAS-Cog11 (word recall, commands, constructional praxis, naming objects and fingers, ideational praxis, orientation, word recognition, spoken language ability, comprehension of spoken language, word-finding difficulty, and remembering test instructions), the ADAS-Cog13 includes a test of delayed word recall and a number cancellation task. The test comprises 9 performance items and 4 clinician-rated items, with a total score ranging from 0 (no impairment) to 85 (severe impairment). Therefore, higher scores indicate more severe cognitive impairment. The assessment will be performed as per Appendix 2 Schedule of Assessment.

[figure not shown]
#### 6.2.1.3 Pharmacodynamic Variables

Pharmacodynamic variables will consist of ERP P300 assessments through electroencephalogram (EEG) assessments. ERP P300 should be performed when the subject is not experiencing interfering motor disturbances that might affect the quality of ERP P300 data; if necessary, the time window for ERP P300 assessments can be extended.

[figure not shown]
ERP P300 is a method of recording brain activity elicited by external stimuli, e.g., an oddball auditory stimulus, and is a well-established functional biomarker, particularly of working memory access (Ally et al, 2006). ERP P300 is characterized by a stereotyped series of voltage deflections occurring after the respective odd tone to be counted, with early features (< 100 msec) corresponding to unconscious sensory transmission (auditory cortex, N100), and later features produced by cognitive processing in the ventral attentional network, i.e., P300, referring to the large positive deflection at roughly 300 msec in healthy adults (young or elderly). The P300 latency is sensitive to detecting reduced synaptic transmission related to cognitive decline in AD patients and other dementias (Olichney et al, 2011).

The EEG assessment will be performed as per Appendix 2 Schedule of Assessment.

[figure not shown]
Confidential Page 16 of 57

Confidential Page 17 of 57

Confidential Page 18 of 57

Confidential Page 19 of 57

# **6.4** Safety Measures

#### **6.4.1** Adverse Events

The investigator and any designees are responsible for detecting, documenting, and recording events that meet the definition of an AE or SAE and remain responsible for following up AE (see Section 6.4.1.3).

#### 6.4.1.1 Definitions

An AE is any untoward medical occurrence in a study subject which does not necessarily have a causal relationship with this treatment. An AE can therefore be any unfavorable and unintended sign (including a clinically significant abnormal laboratory finding), symptom, or disease (new or exacerbated), temporally associated with the use of the IMP, whether or not considered related to the IMP.

Events meeting the definition of AE include:

- Any abnormal laboratory test results (hematology, clinical chemistry, or urinalysis) or other safety assessments (e.g., ECGs, vital signs measurements), including those that worsen from baseline, considered clinically significant in the medical and scientific judgment of the investigator (i.e., not related to progression of underlying disease).
- Exacerbation of a chronic or intermittent pre-existing condition including either an increase in frequency and/or intensity of the condition.
- Signs, symptoms, or the clinical sequelae of a suspected drug-drug interaction.
- Signs, symptoms, or the clinical sequelae of a suspected overdose of either study treatment or a concomitant medication. Overdose per se will not be reported as an AE/SAE unless it is an intentional overdose taken with possible suicidal/self-harming intent. Such overdoses should be reported regardless of sequelae.

Events not meeting the definition of AE include:

- Any clinically significant abnormal laboratory findings or other abnormal safety assessments that are associated with the underlying disease, unless judged by the investigator to be more severe than expected for the subject's condition.
- The disease/disorder being studied or expected progression, signs, or symptoms (clearly defined) of the disease/disorder being studied, unless more severe than expected for the subject's condition.

Confidential Page 20 of 57

- Medical or surgical procedure (e.g., endoscopy, appendectomy): the condition that leads to the procedure is the AE.
- Situations in which an untoward medical occurrence did not occur (social and/or convenience admission to a hospital).
- Anticipated day-to-day fluctuations of pre-existing disease(s) or condition(s) present or detected at the start of the study that do not worsen (note: preexisting conditions will be recorded as part of the subject's medical history).

#### **6.4.1.2** Assessment of Adverse Events

Each AE will be assessed by the investigator with regard to the categories discussed in the sections below.

#### **Intensity**

The investigator will assess all AEs for severity in accordance with the following standard ratings:

- Mild: Ordinarily transient symptoms, does not influence performance of subject's daily activities. Treatment is not ordinarily indicated or may be minimal.
- Moderate: Marked symptoms, sufficient to make the subject uncomfortable. Moderate influence on performance of subject's daily activities. Treatment may be necessary to alleviate symptoms.
- Severe: Symptoms cause considerable discomfort. Substantial influence on subject's daily
  activities, or significantly affects clinical status. May be unable to continue in the study
  and intensive treatment may be necessary.

When changes in the intensity of an AE occur more frequently than once a day, the maximum intensity recorded for the event should be noted.

Note: an event is defined as serious when it meets at least 1 of the predefined outcomes as described in the definition of an SAE (see later), NOT when it is rated as severe.

#### **Causality**

The investigator will assess the causality/relationship between the AE and IMP/study procedure. One of the categories described in Table 2 should be selected based on medical judgment, considering the definitions below and all contributing factors. In this study AEs will be considered related to IMP/study procedure if causality is ascribed as either related, probably related, or possibly related.

Confidential Page 21 of 57

Table 2. Assessment of Relationship of Adverse Events to IMP/Study Procedure

Related	A clinical event, including laboratory test abnormality, which occurs in a plausible time relationship to treatment administration, and which concurrent disease or other drugs or chemicals cannot explain. The response to withdrawal of the treatment (dechallenge*) should be clinically plausible. The event must be definitive pharmacologically or phenomenologically, using a satisfactory rechallenge† procedure if necessary.	
Probably related	A clinical event, including laboratory test abnormality, with a reasonable time sequence to administration of the treatment, unlikely to be attributed to concurrent disease or other drugs or chemicals, and which follows a clinically reasonable response on withdrawal (dechallenge). Rechallenge information is not required to fulfil this definition.	
Possibly related	A clinical event, including laboratory test abnormality, with a reasonable time sequence to administration of the treatment, but which could also be explained by concurrent disease or other drugs or chemicals. Information on treatment withdrawal may be lacking or unclear.	
Unlikely to be related	A clinical event, including laboratory test abnormality, with a temporal relationship to treatment administration which makes a causal relationship improbable, and in which other drugs, chemicals or underlying disease provide plausible explanations.	
Unrelated	A clinical event, including laboratory test abnormality, with little or no temporal relationship with treatment administration. May have negative dechallenge and rechallenge information. Typically explained by extraneous factors (e.g., concomitant disease, environmental factors or other drugs or chemicals).	

\*Dechallenge is when a drug suspected of causing an AE is discontinued. If the symptoms of the AE disappear partially or completely, within a reasonable time from drug discontinuation, this is termed a positive dechallenge. If the symptoms continue despite withdrawal of the drug, this is termed a negative dechallenge. Note that there are exceptions when an AE does not disappear upon discontinuation of the drug, yet drug-relatedness clearly exists (for example, as in bone marrow suppression, fixed drug eruptions, or tardive dyskinesia).

†Rechallenge is when a drug suspected of causing an AE in a specific subject in the past is readministered to that subject. If the AE recurs upon exposure, this is termed a positive rechallenge. If the AE does not recur, this is termed a negative rechallenge.

The investigator may change his/her opinion of causality in light of follow-up information and send an SAE follow-up report with the updated causality assessment.

The causality assessment is one of the criteria used when determining regulatory reporting requirement.

Confidential Page 22 of 57

#### **Seriousness**

An SAE is defined as any untoward medical occurrence that at any dose:

- Results in death.
- Is life-threatening; this means that the subject was at risk of death at the time of the event; it does not mean that the event hypothetically might have caused death if it were more severe.
- Requires hospitalization or prolongation in existing hospitalization; in general, hospitalization signifies that the participant has been detained (usually involving at least an overnight stay) at the hospital or emergency ward for observation and/or treatment that would not have been appropriate in the physician's office or outpatient setting.

Complications that occur during hospitalization are AEs. If a complication prolongs hospitalization or fulfils any other serious criteria, the event is serious. When in doubt as to whether hospitalization occurred or was necessary, the AE should be considered serious. Hospitalization for elective treatment of a pre-existing condition that did not worsen from baseline is not considered an AE.

• Results in persistent or significant incapacity or substantial disruption of the ability to conduct normal life functions.

This definition is not intended to include experiences of relatively minor medical significance such as uncomplicated headache, nausea, vomiting, diarrhea, influenza, and accidental trauma (e.g., sprained ankle) which may interfere with or prevent everyday life functions but do not constitute a substantial disruption.

- Is a congenital anomaly or birth defect, or
- Is another important medical event (see below)

Important medical events that do not result in death, are not life-threatening or do not require hospitalization may be considered SAEs when, based on appropriate medical judgment, they may jeopardize the subject and may require medical or surgical intervention to prevent one of the outcomes listed above. Examples of such medical events include invasive or malignant cancers, intensive treatment in an emergency room or at home for allergic bronchospasm, blood dyscrasias or convulsions that do not result in hospitalization, or development of drug dependency or drug abuse.

A distinction should be drawn between serious and severe AEs. Severity is a measure of intensity whereas seriousness is defined by the criteria above. For example, a mild degree of gastrointestinal bleeding requiring an overnight hospitalization for monitoring purposes would be considered an SAE but is not necessarily severe. Similarly, an AE that is severe in intensity is not necessarily an SAE. For example, headache may be assessed as severe in intensity but would not be considered an SAE.

Confidential Page 23 of 57

Medical and scientific judgment should be exercised in deciding if an AE is serious and if expedited reporting is appropriate.

#### 6.4.1.3 Follow-up of Adverse Events

All AEs experienced by a subject, irrespective of the suspected causality or seriousness, will be monitored until the event has resolved, until any abnormal laboratory values have returned to baseline or stabilized at a level acceptable to the investigator and Medical Monitor, until there is a satisfactory explanation for the changes observed or until the subject is lost to follow-up.

All AEs/SAEs that are still present after the last study drug administration (including AEs that have led to premature discontinuation), will be followed-up at the Safety follow-up visit. In case the AE/SAE is still ongoing after that timepoint, this will be followed up until its resolution or until otherwise agreed between the Sponsor and the investigator.

Additional safety data collected after the Safety follow-up visit to follow-up the ongoing AE will not be included into the clinical database, if this was already locked; therefore, the clinical database lock will not be delayed due to this situation. Any SAE will be followed up, if needed, after clinical database lock, and the information will be only stored in the safety database.

#### 6.4.2 Pregnancy

Female subjects who become pregnant during the study will be withdrawn.

Abnormal pregnancy outcomes (e.g., spontaneous abortion, fetal death, stillbirth, congenital anomalies, ectopic pregnancy) are considered SAEs.

#### 6.4.3 Clinical Laboratory Assessments

The assessment will be performed as per Appendix 2 Schedule of Assessment. The following laboratory variables will be determined as outlined in Table 3 below:

**Table 3.** Clinical Laboratory Assessments

Test	Parameters		
Hematology	CBC	Leukocytes (WBC)	
	Hb1Ac	Differential WBC	
	Hemoglobin	Platelets	
	Hematocrit		
	Erythrocytes (RBC)		

Confidential Page 24 of 57

Biochemistry	Sodium	GGT
	Potassium	CPK
	Magnesium	Total bilirubin
	FSH (post-menopausal females only) a	Total protein
	Calcium	Albumin
	Chloride	Total Cholesterol
	Glucose	Low-density lipoprotein
	Creatinine	High-density lipoprotein
	ALP	Triglycerides
	AST	TSH, fT3 and fT4 a
	ALT	,
Coagulation	INR	aPTT
	PT	
Serology	HBsAg a	HIV type 1 or type 2 a
	HCV a	
Urinalysis	pH glucose	nitrite
•	ketones	protein
	specific	bilirubin
	gravity	blood
	HCG (females	
	of child-	
	bearing	
	potential only)	

AST = aminotransferase; ALP = alkaline phosphatase; ALT = alanine transaminase; CBC = complete blood count; CPK = creatine phosphokinase; FSH = follicle-stimulating hormone; GGT = gamma-glutamyl transferase; Hb1Ac = glycated hemoglobin; HBsAg = hepatitis B surface antigen; HCG = human chorionic gonadotropin; HIV = human immunodeficiency virus; INR = international normalized ratio; PT = prothrombin time; aPTT = activated partial thromboplastin time; RBC = red blood cells; fT3 = free triiodothyronine; fT4 = free thyroxine; TSH = thyroid-stimulating hormone; WBC = white blood cells.

a Measured only at Screening for eligibility; not included in subsequent safety labs.

Any value outside the normal range will be flagged for clinical interpretation by the investigator or designee at the site. In this study, ALT or AST > 2 times the upper limit of normal, or Child-Pugh Class B and C (i.e., including total bilirubin, albumin, and INR values), will be exclusionary. For transaminase liver enzymes, a repeat laboratory assessment may be performed if outside of the normal range. If the transaminases remain elevated the investigator should consider stopping study medication and withdrawing the subject.

A medical alert for potential Hy's laws cases (possible drug-induced liver injury) will be issued based on lab values and supported by Medical Monitor interpretation.

Criteria for potential Hy's law cases are as follows:

- ALT or AST  $\geq$  3 × ULN AND
- Total bilirubin  $\geq 2 \times ULN \text{ AND}$
- Alkaline phosphatase < 2 × ULN

For the Elevated Liver Tests summary, the list of lab test with criteria will be considered.

Confidential Page 25 of 57

- i) Alanine Aminotransferase (Normal <=ULN, >1 3 x ULN, >3 5 x ULN, >5 10 x ULN, >10 20 x ULN, >20 x ULN)
- ii) Aspartate Aminotransferase (Normal <=ULN, >1 3 x ULN, >3 5 x ULN, >5 10 x ULN, >10 20 x ULN, >20 x ULN)
- iii) Alkaline Phosphatase (Normal <=ULN, >1 2 x ULN, >2 x ULN)
- iv) Bilirubin (Normal <= 2 x ULN, >2 x ULN)
- v) Hy's Law: ALT/AST>=3xULN and BILI>=2xULN (Criteria Not Met, With ALP <2 x ULN, With ALP >=2 x ULN)
- vi) Alkaline Phosphatase >=2 x ULN (Criteria Not Met, With ALT/AST <2X ULN, With ALT/AST >=2X ULN)

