### 1.3 Risk-Benefit Assessment

Whilst qEEG and ERP P300 results in humans are indicative of CNS penetration and target engagement, efficacy in subjects with PDD or DLB (in terms of cognitive, functional, or behavioral improvement) has not been established. Therefore, the benefits to study subjects of participating in this clinical trial are not yet known.

In clinical studies of ATH-1017, single SC administration of 2, 6, 20, 40, 60, and 90 mg in healthy young subjects, and multiple administration of 20, 40, 60, and 80 mg (SC, OD, over 9 consecutive days) in healthy elderly subjects, and 40 mg (SC, OD, over 9 consecutive days) in AD subjects were safe and well tolerated. Injection site reactions included pain, pruritus, and/or erythema, were mild in nature, and resolved without specific therapy. A potential risk for hepatotoxicity identified in nonclinical studies has not been observed in human studies but will be closely monitored in this study. To date, no CNS-specific adverse events have been observed in humans.

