# 5.8 Stopping Criteria

For all subjects, at any time during the study, study treatment should be discontinued and the subject will be withdrawn immediately if any of the following criteria/AEs are recorded:

- ALT or AST  $> 5 \times ULN$  for more than 2 weeks
- ALT or AST  $> 8 \times$  upper limit of normal (ULN)
- ALT or AST > 3 × ULN and total bilirubin > 2 × ULN, or international normalized ratio [INR] > 1.5
- ALT or AST  $> 3 \times$  ULN with symptoms (the appearance of fatigue, nausea, vomiting, right upper quadrant pain or tenderness, fever, rash, and/or eosinophilia > 5%)
- AEs:
  - Any SAE confirmed as probably or definitely related to the IMP
  - Any AE of severe intensity confirmed as probably or definitely related to the IMP and associated with clinically significant findings
     (Note: causality as determined by the Sponsor)

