#### 8.4.2 Laboratory parameters

Laboratory parameters and vital signs will be summarized by visit. Frequencies of high and low values with respect to the normal range will be displayed, as will shift tables comparing results at each treatment visit.

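### The SAP's liver table labels bilirubin up to 2 x ULN as normal, and no other table specified in the SAP counts values between 1 and 2 x ULN

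*SAP*

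**What the plan says.** SAP 6.4.3 sets out an Elevated Liver Tests summary with six rows. Dashes in the bands appear to have been lost when the PDF was read.

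- Row i, ALT: "Alanine Aminotransferase (Normal <=ULN, >1 3 x ULN, >3 5 x ULN, >5 10 x ULN, >10 20 x ULN, >20 x ULN". Row ii, AST, has the same bands.
- Row iii, ALP: "Alkaline Phosphatase (Normal <=ULN, >1 2 x ULN, >2 x ULN".
- Row iv, bilirubin: "Bilirubin (Normal <= 2 x ULN, >2 x ULN".
- Row v: "Hy's Law: ALT/AST>=3xULN and BILI>=2xULN", split by ALP.
- Row vi: ALP at or above 2 x ULN, split by ALT/AST.

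Protocol 1.3 explains why liver output matters: "A potential risk for hepatotoxicity identified in nonclinical studies has not been observed in human studies but will be closely monitored in this study".

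For laboratory data in general, Protocol 8.4.2 states: "Frequencies of high and low values with respect to the normal range will be displayed, as will shift tables". SAP 10.6.2 specifies n, mean, median, SD, minimum and maximum by analyte, visit and treatment group, plus full listings. It specifies no high/low counts and no shift tables. The note in SAP Section 6 says that early stopping leaves the safety output as planned and makes only efficacy and biomarker analyses exploratory. SAP Section 8, which records departures from the protocol, does not mention these laboratory tables.

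**The concern.** In a table meant to show raised liver tests, one analyte has a normal category that extends to twice the upper limit. A reader would take the word in the bilirubin row to mean what it means in the three rows above it, and would conclude that subjects with mildly raised bilirubin had none.

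A label fault in one table matters little if another table counts the same values correctly. Here the tables that would do so are promised in the protocol but missing from the SAP. Both gaps fall on the one organ toxicity that the protocol's risk-benefit section says will be closely monitored.

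**Working it through.** The plan gives no figure to reproduce, so the check is to run boundary values through the categories as written.

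**Bilirubin, rows iv and v.** Row iv rule: normal if the value is at most 2 x ULN, otherwise raised. Row v bilirubin part: met if the value is at least 2 x ULN.

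| Bilirubin (x ULN) | Above ULN? | Row iv category | Row v bilirubin part |
|---|---|---|---|
| 1.00 | no | Normal | not met |
| 1.01 | yes | Normal | not met |
| 1.50 | yes | Normal | not met |
| 1.99 | yes | Normal | not met |
| 2.00 | yes | Normal | met |
| 2.01 | yes | >2 | met |

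Four of the six test values are above ULN and labelled normal. The ALP rule applied to 1.50 gives the >1 to 2 band, so the same multiple of ULN is normal for one analyte and raised for another. At exactly 2.00 rows iv and v disagree: a subject who also has ALT or AST of at least 3 x ULN would be a Hy's law case in row v and normal in row iv.

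The same mismatch of > and >= arises at two other single points. ALT or AST of exactly 3.00 falls in >1 to 3 but meets the row v limit. ALP of exactly 2.00 falls in >1 to 2 but meets row vi. In both cases the value is still shown as raised, so these are matters of tidiness.

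**ALT/AST, rows i and ii.** Values of 7.9, 8.01 and 9.9 x ULN all fall in the >5 to 10 band. The number above the 8 x ULN criterion in Protocol 5.8 cannot be read from the table, but no value above 1 x ULN is called normal.

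**Where else bilirubin between 1 and 2 x ULN would appear.**

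- High/low frequencies: promised in Protocol 8.4.2, not specified in SAP 10.6.2.
- Shift tables: the same.
- Continuous summaries in SAP 10.6.2: the maximum reveals at most the single highest value per arm and visit.
- Listings in SAP 10.6.2: every value is present, but none is counted.

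No table specified in the SAP therefore counts these values as raised.

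**The case against.** The strongest reply is that 2 x ULN is the bilirubin level the documents act on: above 2 x ULN in Protocol 5.8, and at or above it in the Hy's law criteria. Counts above 2 x ULN and the Hy's law row are correct as written. The liver table is also additional to what the protocol's safety-summary sections ask for, and sites are told of any out-of-range result. All of this stands and keeps the point minor. It justifies a cut at 2 x ULN, but not calling everything below that cut normal.

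It can also be said that the omission in SAP 10.6.2 is inferred from silence. That section gives a denominator for percentages, which suggests that some categorical laboratory output was intended, and Section 8 says analyses will be minimal. This is a fair reason to ask for clarification. It does not settle the matter, because no categorical output is specified there and Section 6 says the safety summaries are retained.

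A reader might go further and infer that ALT and AST are misreported because the >5 to 10 band spans 8 x ULN. The documents do not support that. Every raised value sits in a raised band, so the loss is one of resolution. The 8 x ULN limit is an individual stopping criterion, and Protocol 5.8 requires any case meeting it to be reported to and discussed with the Medical Monitor. Nothing says this table is meant to count such cases. Nor do the SAP's summaries rest on means alone: maxima and full listings are specified, and in small arms the listings can be read directly.

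**Conclusion.** The concern holds for bilirubin and for the missing Protocol 8.4.2 tables, and it is minor. Values above 1 and up to 2 x ULN are tabulated as normal, and exactly 2 x ULN is classified inconsistently between rows iv and v. With the high/low frequencies and shift tables absent and their removal undeclared, these values can be seen only in listings and, in part, in the maxima.

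The number of subjects affected cannot be stated. The documents give no rate of mildly raised bilirubin. Applying an assumed rate to the planned 75 subjects would describe a trial that the SAP says stopped early with fewer enrolled. The conclusion rests on reading the SAP text literally, and on SAP 10.6.2 being the complete specification of the general laboratory tables. It implies no view on which bilirubin or transaminase limit is clinically right.

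**What to change.** 1. In SAP 6.4.3 row iv, use three categories: normal at or below ULN, >1 to <2 x ULN, and >=2 x ULN. All six test values above are then correctly placed, and the top category agrees with the bilirubin part of row v. Any other wording that separates >1 x ULN from normal and aligns the boundary with row v would also serve. Protocol 5.8 uses >2 x ULN, so a footnote should state which convention the table follows.
2. In SAP 10.6.2, restore the high/low frequencies and shift tables of Protocol 8.4.2. If they are not to be produced, list their removal in SAP Section 8 with the reason.
3. Optionally, split the ALT/AST >5 to 10 band at the protocol's existing 8 x ULN limit, and use one convention for > and >= across the rows.

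The cost is a few table-shell and programming edits. The data are already collected, and no further assessments are needed.
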